For test subjects, total circumference measurements decreased progressively from baseline at each of the three subsequent evaluation points culminating in a mean decrease of 4.62 inches by 2 weeks post-procedure evaluation. For placebo subjects, the magnitude of the change was constant for all three subsequent evaluation points relative to baseline, indicating lack of any change in total circumference measurements beyond week 2 evaluation relative to baseline. Additionally, the magnitude of the changes relative to baseline for placebo group subjects were notably less than the respective changes for test group subjects relative to baseline. Considered together, these findings support progressive effectiveness of the Erchonia® Obesity Laser procedures over time compared with placebo.

At completion of study procedure administration, the subject was asked to rate how satisfied he or she was with any overall perceived change in the appearance of the hips-waist-upper abdomen area using the following five-point scale: Very Satisfied; Somewhat Satisfied; Neither Satisfied nor Dissatisfied; Not Very Satisfied; Not at All Satisfied. 79% of test group subjects reported being 'Satisfied' ('Very Satisfied' or 'Somewhat Satisfied') with the study outcome compared with 16% of placebo subjects.

ADVERSE EVENTS

No adverse event occurred for any subject throughout duration of the clinical study. There was no change in skin markers in the treated body areas, and no notable deviation from baseline diet, exercise or concomitant medication use for any study subject.

CONCLUSION

The Erchonia® Obesity Laser is an effective tool for reducing circumference measurements of the hips-waist-upper abdomen in individuals with Body Mass Index (BMI) between 30 kg/m² and 40 kg/m² over a 4-week period.

STUDY DESIGN

This clinical study is a prospective open-label design with post-study independent blinded outcome analysis to evaluate the efficacy of the Erchonia® CFL Laser in providing noninvasive fat reduction in the submental area. As such, all enrolled subjects will receive active study treatments, and therefore, randomization to procedure group is not applicable.

STUDY BLINDING

As all subjects in this study will receive active procedure administrations with the Erchonia® CFL, neither subjects nor treating investigators will be blinded.

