The investigator will commence by presenting and reviewing in detail the items in the informed consent form with the individual and answer any questions. To proceed, the individual must willingly sign the informed consent form.

ASSIGNMENT OF SUBJECT ID

The subject will be assigned a unique subject identification number based upon his or her order of entry into the study.

Additional information about the informed consent and subject ID number assignment is contained in a later section of the protocol titled, “SAFETY AND CONFIDENTIALITY ISSUES.”

STUDY QUALIFICATION EVALUATION: INCLUSION/EXCLUSION CRITERIA

INCLUSION CRITERIA

To be eligible for participation in this study, a subject must satisfy each of the following.

- Male or female 18 to 65 years of age, inclusive.
- Submental and submandibular skin fold thickness > 1cm (measured by caliper).
- Subject agrees to maintain his/her weight (i.e., within 5%) by not making any major changes in diet or exercise routine during the course of the study.

- Subject agrees to abstain from partaking in any treatment to promote body contouring and/or weight loss during the course of study participation. Such treatments include, but are not limited to:
 - over-the-counter and/or prescription medications; dietary/herbal supplements and appetite suppressants.
 - weight loss programs/diet plans.
 - surgical procedures for sculpting of the chin fat pad/weight loss, e.g. submental lipectomy, lap bands
- Subject has signed a written informed consent form.

EXCLUSION CRITERIA

A subject who satisfies any of the following criteria will be excluded from study participation:

- Evidence of any cause of enlargement in the submental area other than localized subcutaneous fat, such as swollen lymph nodes or ptotic submandibular glands.
- Treatment with dermal fillers, radiofrequency or laser procedures, or chemical peels in the neck or chin area (below the mandible) within the past 6 months.
- Botulinum toxin or other aesthetic drug injections within the neck or chin area (below the mandible) within the past 6 months.
- History of a fat reduction procedure (e.g., liposuction, surgery, lipolytic agents, etc.) or implant in or adjacent to the area of intended treatment.
- Any dermatological conditions, such as scars in the location of the treatment area that may interfere with the treatment or evaluation.
- Active implanted device such as a pacemaker, defibrillator, or drug delivery system.

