WEEK 4 EVALUATION: TREATMENT ENDPOINT: AT THE TIME OF TREATMENT PROTOCOL END

Following the final treatment at completion of the 4 weeks of study treatment administrations with the Erchonia® CFL, the following will be recorded on the provided Case Report Forms.

- Photographs
- Skinfold caliper measurements (mm)
- Body Mass Index (BMI) Calculation
- Subject Satisfaction with Study Outcome

WEEK 16 EVALUATION: STUDY EFFICACY ENDPOINT: 12 WEEK POST TREATMENT ADMINISTRATION END

Twelve (12) weeks following the completion of the 4-week treatment administration protocol, the following will be recorded on the provided Case Report Forms. These recordings will form the study endpoint data set from which change from baseline will be evaluated with respect to

assessing study outcome.

- Photographs
- Skinfold caliper measurements (mm)
- Body Mass Index (BMI) Calculation
- Subject Satisfaction with Study Outcome

ADVERSE EVENTS

At each evaluation point throughout the clinical study, and at any other time throughout the duration of the clinical trial that is necessary, any and all potential adverse events reported by a subject or observed by an investigator will be recorded on the case report form, and subsequently evaluated by a suitably qualified independent reviewer for determination of relationship to the study treatment and whether or not any corrective action needs to be taken. All potential adverse events recorded will be appropriately reported to the governing IRB, as applicable.

It is unlikely and not expected that any adverse events will result from implementation of this clinical study protocol. Prior clinical trials using low level laser light have not typically yielded any adverse events or reactions. However, potential adverse events that may feasibly occur from application of the Erchonia® CFL include, but are not necessarily limited to: skin irritation, discoloring, rash, indentations and infection.

PRIVACY AND CONFIDENTIALITY

Records for each subject in this clinical study will be maintained in separate files in a locked filing cabinet at the respective test site. The investigator at the test site will be responsible for ensuring that all records for a subject pertaining to his or her participation in the clinical study are stored in that subject's file at all times other than when information is being recorded on them.

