Copies of all of the subject case report forms will be made and supplied to Erchonia Corporation who will maintain these copies in a separate clinical study file that is kept in a locked filing cabinet at their premise. The original records will be maintained at the respective test sites.

Subjects' identities will be kept confidential by assigning each subject a subject ID upon acceptance into the study. The subject ID will comprise the investigator's first and last name initials followed by a three-digit number determined according to the subject's order of entry into the study. The first test site will be assigned a range of numbers from 001 to 100. The second test site will be assigned a range of numbers from 101 to 200. For example, the eighth subject to be enrolled at the first test site under PI [name] would have a subject ID of JB008. Neither the study Sponsor, Monitor, biostatistician, Independent Blinded Evaluators, nor any other pertinent party will receive any additional identifying information about a subject and will therefore have no way of linking a Subject ID to a particular subject and his or her study results.

STATISTICAL ANALYSIS PLAN

STUDY POPULATIONS

The following two study populations will be evaluated:

1. Intent-to-Treat (ITT) Population

Primary analysis of efficacy will be according to the intent to treat (mITT) analysis, including all consented and enrolled subjects.

2. Per Protocol Population

Secondary analysis of efficacy to confirm the findings of the primary analysis will be conducted on the Per Protocol population, comprised of all subjects who completed the study per protocol inclusive of all assessment visits and activities and the full 4-week, 8-treatment administration protocol.

3. Handling of Missing Data

Missing data values will be imputed using regression analysis imputation methodology under the assumption of the data missing at random (MAR), provided that the assumption of the data being MAR can be supported as has been found through prior Erchonia studies and demonstrated through the following means, the first two of which are already established by the study design:

1. As there is no placebo group in this clinical study design, subjects are aware that they are receiving active study treatments, and therefore, subject lost to follow up cannot be attributed to potential study unblinding.

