
In consideration of this primary efficacy outcome assessment, a clinically important outcome is defined as at least 2 of the 3 Independent Blinded Evaluators (i.e., 2 out of 3, or 3 out of 3) correctly identifying the order of a subject's Pre-Treatment (Baseline) and Week 16 (Endpoint) 12 Weeks Post-Final Treatment photograph for 80% or more of subjects.

This clinically important minimum upper limit criteria of 80% was selected to be identical to the respective primary efficacy endpoint assessment parameters from the clinical studies for the ZELTIQ CoolSculpting System (K151179), and SculpSure (K171992) whose outcomes successfully supported FDA clearances for the same indication as intended to be supported by the outcome of the current clinical study protocol.

HYPOTHESES

The null and alternative hypotheses for the Primary Efficacy Endpoint are the following:

Null Hypotheses: The overall responder rate will be less than 80%.

$$H_0: \mu A < 80\%$$

Alternative Hypothesis: The overall responder rate will be 80% or greater.

$$H_0: \mu A \geq 80\%$$

PRIMARY EFFICACY OUTCOME ANALYSIS POPULATION

Determination of primary efficacy outcome success will be according to analysis of the outcome

for the subject ITT population as the primary analysis population. Primary efficacy outcome success will also be evaluated for the study Per Protocol population as a secondary analysis to provide support for and confirm the outcome of the primary analysis performed on the ITT subject population.

PRIMARY EFFICACY OUTCOME STATISTICAL EVALUATION

Primary study efficacy will be evaluated at Week 16, 12 Weeks Post-Final Treatment administration relative to Baseline (Pre-Treatment).

Primary efficacy outcome success will be evaluated via Responder Rate Analysis, wherein:

- (i) An individual subject is defined as a Study Responder if at least 2 of the 3 Independent Blinded Evaluators correctly identify the subject's post-treatment photograph, and
- (ii) Overall study success is defined as a minimum responder rate of 80%.

To determine primary efficacy outcome success, the following process will be followed:

1. The percentage of individual Study Responders will be calculated to determine the responder rate.
2. If the calculated responder rate is 80% or greater ($\geq 80\%$), it will be concluded that primary efficacy success has been demonstrated.

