3. If the calculated responder rate is less than 80% ($< 80\%$), it will be concluded that primary efficacy success has not been demonstrated.

SECONDARY EVALUATIONS The secondary efficacy outcomes of submental skinfold and submental skinfold thickness, and subject satisfaction with treatment outcome will be assessed for each of the ITT and Per Protocol analysis populations, as applicable. As these secondary outcomes are provided as supportive evidence for the primary efficacy outcome only and the Sponsor **does not intend to seek clearance for any claims based on findings of these secondary efficacy outcomes**, the findings will be presented descriptively only as means, standard deviations, medians, and ranges for the continuous data and as number (N) and percentage (%) of the total for categorical data and will be presented in table and chart format, as applicable. Statistical analysis of change will not be performed.

- Submental skinfold and submental skinfold thickness measurements (mm) data will be recorded at each of the Pre-Treatment (Baseline), Week 4 (Treatment End), and Week 16 (12 Weeks Post-Treatment End) visits.
- Subject satisfaction with study outcome ratings will be recorded at each of the Week 4 (Treatment End) and Week 16 (12 Weeks Post-Treatment End) visits.

'Positive' subject satisfaction with treatment outcome response is predefined as the sum of 'Very Satisfied' and 'Somewhat Satisfied' responses.

- Additionally, comparison of the mean, standard deviation, median, and range of Body Mass Index (BMI) recording at each of Pre-Treatment (Baseline), Week 4 (Treatment End), and Week 16 (12 Weeks Post-Treatment End) visits will be compared descriptively to confirm that changes in body BMI did not contribute to the study outcome.

SAFETY ANALYSES

Safety analyses will be based on all subjects who signed informed consent and were enrolled in the study.

Safety will be assessed by evaluating observed and/or reported adverse events.

INFORMED CONSENT

- Informed consent will be an agreement between the individual investigator and each subject, having the capacity to understand and make an informed decision. Consent will be obtained prior to each potential subject's participation in this study.
- Each subject participating in this study will be made aware of the fact that his or her participation involves research and the intent of the research, the expected duration of participation and a description of the procedures that will be followed.

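### Visit-level BMI summaries can show a general weight change but cannot confirm that BMI change did not contribute to the responder rate, because they never use responder status (minor)

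*Combined protocol and SAP*

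**What the plan says.** - **BMI check.** In the SAP, Secondary Evaluations, the last bullet sets out BMI mean, SD, median and range at Baseline, Week 4 and Week 16. These "will be compared descriptively to confirm that changes in body BMI did not contribute to the study outcome".
- **Descriptive only.** For the secondary outcomes the same section states: "Statistical analysis of change will not be performed".
- **Outcome.** In Primary Efficacy Outcome Statistical Evaluation, "An individual subject is defined as a Study Responder if at least 2 of the 3 Independent Blinded Evaluators correctly identify" the post-treatment photograph. Success is an observed responder rate of at least 80%.
- **Design.** Under Study Design, "all enrolled subjects will receive active study treatments". There is no comparison group.
- **Weight controls.** Under Inclusion Criteria, subjects agree to keep weight within 5%, to make no major diet or exercise change, and to avoid treatments for weight loss or body contouring.
- **Data.** BMI is recorded for each subject before treatment, at Week 4 and at Week 16. The Week 16 Evaluation section calls its recordings "the study endpoint data set from which change from baseline will be evaluated". It names no BMI-change statistic and does not relate BMI change to response.

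**The concern.** Evaluators judge which photograph came after treatment. A subject who lost weight may show a slimmer submental area whatever the laser did, and no untreated group shows how often that happens. The sponsor evidently sees this, because it plans a BMI check.

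The check does not match the conclusion attached to it. Response is a property of each subject, while the planned BMI statistics describe the whole group at each visit. To say that BMI change did not contribute, one must at least know who lost weight and whether those subjects responded. If the summaries look flat and the report then says that a BMI contribution has been ruled out, that statement will rest on an analysis that could not have shown otherwise.

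**Working it through.** The plan gives no BMI figure to reproduce. From the documents: 35 enrolled (Sample Size), an 80% success threshold, and a 5% weight limit. Adult height is fixed, so percent BMI change equals percent weight change. All other inputs are assumptions and are marked as such.

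**1. Threshold.** 0.80 × 35 = 28 responders.

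**2. Who responded does not enter the planned statistics.** Mean, SD, median and range depend on the BMI values alone. Assume 7 subjects lost weight and r of them responded, with 28 responders in all. The rate in the other 28 is (28 − r)/28:

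| r of 7 responding | Rate in other 28 | Exact 95% CI |
|---|---|---|
| 7 | 21/28 = 75.0% | 55% to 89% |
| 6 | 22/28 = 78.6% | 59% to 92% |
| 5 | 23/28 = 82.1% | 63% to 94% |
| 0 | 28/28 = 100% | 88% to 100% |

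The planned BMI summaries are identical in all four rows.

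**3. What the summaries would show.** Assume Baseline BMI has mean 28 and SD 4. If k of 35 subjects lose a fraction f, the mean moves by −k × f × 28/35.
- k = 7, f = 4%: −7 × 0.04 × 28/35 = −0.22 kg/m². All 35 losing 0.8% gives the same shift (0.008 × 28 = 0.22).
- k = 7, f = 2%: −0.11. k = 10, f = 5%: −0.40.
- In 20,000 simulated samples with k = 7 and f = 4%, the median BMI moved by −0.13 (95% range −0.94 to 0.00) and the SD by 0.00 (−0.17 to +0.13). Minimum and maximum were both unchanged in 57% of samples.

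The mean and median therefore carry some signal, but they do not separate a small loss in everyone from a larger loss in a few.

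**4. Flat summaries with real individual change.** Take 35 constructed BMI values (assumed, mean 29.0, SD 3.99) and reassign them among subjects so that nobody changes by more than 5%. Mean, SD, median, minimum and maximum are the same at both visits, yet 12 subjects lose (1.0 kg/m² on average), 12 gain and 11 are unchanged. With 28/35 responders, this one BMI table fits each of the following:
- 12/12 of the losers and 16/23 of the others (100% − 69.6% = +30 points);
- 10/12 and 18/23 (83.3% − 78.3% = +5 points);
- 5/12 and 23/23 (41.7% − 100% = −58 points).

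**5. How much it could move the result.** Chance of at least 28 of 35 responders, as the sum of two binomials. The responder probabilities are assumed:

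| Other subjects respond with probability | 50% | 60% | 70% |
|---|---|---|---|
| No weight losers | 0.03% | 1.0% | 13% |
| 7 losers, each responding with probability 80% | 0.2% | 3% | 19% |
| 7 losers, each responding with probability 95% | 0.5% | 6% | 32% |

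With 30 subjects (24 or more needed, 6 losers at 95%) the pattern is the same: 0.07%, 1.7% and 16% without losers, against 0.9%, 8% and 34% with them.

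**6. What a subject-level table could show.** The extreme case in step 2 is 7/7 against 21/28, which gives a two-sided Fisher p of 0.30. If the true rates were 95% and 70%, a two-sided 5% Fisher test would detect the difference about 3% of the time.

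**The case against.** The strongest reply is that this is a supporting item and changes no decision. Success rests only on the observed responder rate, no claim is sought on the secondary outcomes, and the plan is deliberately descriptive. That stands, and it is why the point is minor.

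The entry agreements go further than the 5% figure, because they also cover diet, exercise and weight-loss treatment. They make 7 to 10 subjects losing 2% to 5% less likely, and the documents give no frequency for such losses. This also stands. But these are agreements made at entry. No analysis counts who stayed within them.

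Step 2 can be called nearly a tautology, since any group summary is blind to who responded, and 28/35 was chosen to sit on the threshold. It shows the logic and does not estimate a bias. The logic is enough here, because the issue is whether the planned statistics can support the word *confirm*.

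Finally, a subject-level table has little discriminating power (step 6). That is true. It is a reason to change the wording first and to treat the table as a flag.

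**Conclusion.** The point holds as a minor one. The planned summaries can reveal a general weight loss. They cannot show whether the subjects who lost weight were the responders, so they cannot confirm that BMI change did not contribute. This follows from how the statistics are defined and needs no assumption about BMI.

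The size figures do rest on assumptions: 7 subjects losing weight, BMI mean 28 and SD 4, and the responder probabilities in step 5. They show that the matter counts when the result is already near 80%.

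Three stronger readings are tempting, and the documents do not support them:
- *Weight loss could carry an ineffective device to success.* Even under the assumed 95%, seven losers lift the chance only to 0.5% when the others respond half the time, and to 6% at 60%.
- *Weight is uncontrolled, or the BMI check is useless.* The entry agreements exist, and the means and medians would show a general loss.
- *The Per Protocol analysis ignores weight.* That population is those who "completed the study per protocol inclusive of all assessment visits and activities" and the full treatment course. Whether this covers the weight agreement is left unstated, which is missing detail and not evidence of an error.

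**What to change.** 1. **Wording.** In Secondary Evaluations, replace the stated aim of confirming that BMI changes did not contribute with *to assess whether changes in BMI may have contributed*. This carries most of the value.
2. **Subject-level display.** Pre-specify each subject's percent BMI change from Baseline to Week 16 and present it by Week 16 responder status:
   - a listing of all subjects;
   - a simple table of responder rate with exact 95% CI by BMI-change category, with cut-points fixed before the photographs are scored (for example, loss of 2% or more, change under 2%, gain of 2% or more; the 2% is only an illustration);
   - the number of subjects outside ±5%, and the number missing. Use only subjects with BMI and photographs observed at both visits, not imputed values.

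**Cost.** One sentence, one listing and one table, from data already recorded; no new visit or measurement. The downside is imprecision: 21/28 = 75% has an interval of 55% to 89%, and 6/7 = 86% one of 42% to 99.6%. The table can flag a contribution but cannot exclude one, and the report should say so.
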